# 2. OBJECTIVES

Primary Objective:

 To assess the antibody based immune response after vaccination against COVID-19 in patients with cancer treated with immunotherapy and/or chemotherapy as compared to controls

Secondary Objectives:

- To assess adverse events (AEs) after vaccination against COVID-19 in patients with cancer treated with immunotherapy and/or chemotherapy
- To assess durability of the antibody response in patients with cancer treated with immunotherapy and/or chemotherapy
- To analyze the SARS-CoV-2 specific T cell response after vaccination in patients with cancer treated with immunotherapy and/or chemotherapy

Exploratory Objectives:

- To perform in-depth analysis of cellular immune responses in patients with cancer treated with immunotherapy and/or chemotherapy
- To identify baseline (immune) parameters associated with vaccination response in patients with cancer treated with immunotherapy and/or chemotherapy
- To assess the neutralizing capacity of antibodies against SARS-CoV-2 after vaccination in patients with cancer treated with immunotherapy and/or chemotherapy
- To analyze induction of mucosal antibodies against SARS-CoV-2 in mucosal lining fluid samples. To describe the incidence of SARS-CoV-2 infection, outcome of COVID-19 during 12 months after vaccination in patients with cancer treated with immunotherapy and/or chemotherapy
- To analyze SARS-CoV-2-binding antibody concentration after a third vaccination in participants without an adequate antibody response after two vaccinations
- To analyze safety of a third vaccination

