# 4. STUDY POPULATION

# 4.1 Population (base)

# 4.2 Inclusion criteria

To be eligible to participate in this study, a subject must meet all of the following criteria:

- Age of 18 years or older
- Life expectancy > 12 months
- Ability to provide informed consent

Additional criteria for cohort A:

• Partner of a participating patient

Additional criteria for cohort B:

- Histological diagnosis of a solid malignancy
- Treatment with monotherapy immune checkpoint inhibitor (ICI) against Programmed Death 1 (PD1) or its ligand PD-L1 (in curative or non-curative setting)
- Last ICI administration within 3 months of vaccination

Additional criteria for cohort C:

- Histological diagnosis of a solid malignancy
- Treatment with cytotoxic chemotherapy (monotherapy and combination chemotherapy is allowed, as well as a combination with radiotherapy, in curative or non-curative setting)
- Last chemotherapy administration within 4 weeks of vaccination

Additional criteria for cohort D:

- Histological diagnosis of a solid malignancy
- Treatment with a PD1 or PD-L1 antibody in combination with cytotoxic chemotherapy (in curative or non-curative setting)
- Last chemotherapy administration within 4 weeks of vaccination
- Last ICI administration within 3 months of vaccination

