## Correction for drop-out

We expect that a proportion of the participants will already have SARS-CoV-2 antibodies at baseline and will not be evaluable for the primary endpoint. In addition, we anticipate that there will be a drop-out of participants at later time points. Reasons for drop-out may include death or poor performance status as a result of progressive malignancy and/or cancer treatment related AEs. Therefore, we will correct for non-evaluable patients by increasing each cohort with 20%. This means that 246 participants will be recruited in cohorts A, C and D, and 135 participants will be enrolled in cohort B. In total, 873 participants (627 patients and 246 individuals without cancer) will be included.

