#### **10.2 Secondary study parameters**

- Incidence and severity of solicited AEs during 7 days after each vaccination is a key secondary endpoint (see Appendix 1). Frequencies and absolute numbers of mild, moderate and severe solicited AEs per cohort will be listed for the first, second and third vaccination separately.
- The numbers, nature and severity of SAEs graded according CTCAEv5.0 will be listed per cohort.
- Incidence and nature of newly occurring irAEs grade ≥ 3 in cohorts B and D up to 28 days after the second vaccination is the second safety endpoint. irAEs will be graded according CTCAEv5.0. Frequencies and absolute numbers of all newly occurring irAEs grade ≥ 3 that occur between the first vaccination and 28 days after the second vaccination in cohorts B and D will be listed.
- Incidence, nature and severity of AESIs comprise the third safety endpoint. AESIs will be graded according CTCAEv5.0. Absolute numbers and frequencies of all AESIs will be listed per cohort and subdivided by severity.
- Levels of SARS-CoV-2 S-specific IgG antibodies at 28 days after the second vaccination will be compared between each patient cohort and the non-cancer cohort using ANOVA or Kruskal–Wallis one-way analysis of variance, and Welch ttests or Mann-Whitney U tests, depending on the distribution of the data.
- Levels of SARS-CoV-2 S-specific IgG antibodies before the second vaccination and at 6, 11 and 18months after the second vaccination will be measured to assess early antibody response and longevity. GMCs and 95% CIs will be calculated. The absolute numbers and percentages of responders will be reported for each cohort for each time point. Antibody levels before the second vaccination and at 6, 11 and 18 months will be compared between each patient cohort and the non-cancer cohort using ANOVA or Kruskal–Wallis one-way analysis of variance, and Welch t-tests or Mann-Whitney U tests, depending on the distribution of the data.

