#### 10.3 Other study parameters

- Dynamics of SARS-CoV-2 specific antibody concentrations will be analyzed, e.g. by calculating geometric mean fold-rise between baseline and post-baseline time points and antibody decay after day 28.
- In-depth flow-cytometric analyses for functional and phenotypical characterization of SARS-CoV-2 specific cellular responses will be performed by assigning proliferative capacity, cytokine production and phenotypical markers (>25 markers in parallel) in a subset of patients. These descriptive study parameters will not be statistically compared between cohorts.
- Baseline (immune) parameters will be related to vaccination response using univariate analysis.
- As a functional readout, the neutralizing capacity SARS-CoV-2 antibodies will be measured at baseline, 28 days and 6, 11 and 18 months after the second vaccination. Titers will be expressed as GMCs with 95% CIs for each cohort, for each time point.
- To assess induction of a mucosal antibody response, mucosal lining fluid samples will be collected for measurement of SARS-CoV-2-specific antibody concentrations with multiplex immunoassay at baseline and at 28 days after the second vaccination. Additional analyses e.g. neutralizing capacity of mucosal antibodies can be performed.
- Mucosal SARS-CoV-2-specific antibody response will be correlated with serum SARS-CoV-2-specific antibody response.

- Information on incidence of SARS-CoV-2 infection, outcome of COVID-19 during 18 months after the second vaccination will be collected. The number of participants tested, the number of SARS-CoV-2 tests and test results will be reported. For participants with a positive test, information about severity will be presented including hospital admissions, use of oxygen, intensive care admission and mechanical ventilation.
- Levels of SARS-CoV-2 S-specific IgG antibodies before the third vaccination, and at day 28 after the third vaccination will be measured to assess antibody response in participants with an inadequate response to two mRNA-1273 vaccinations.
- Safety of a third mRNA-1273 vaccination in participants with an inadequate response to two mRNA-1273 vaccinations as mentioned under 10.2.

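### The 6-month durability comparison uses only participants sampled at that visit and ignores their day-28 values, so it is biased if the expected cancer-related drop-out is related to antibody level

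*Combined protocol and SAP*

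**What the plan says.** Durability is a secondary objective (section 2): "To assess durability of the antibody response in patients with cancer treated with immunotherapy and/or chemotherapy". Section 10.2 says that antibody levels before the second vaccination and at 6, 11 and 18 months "will be measured to assess early antibody response and longevity". The analysis is a GMC with 95% CI and a responder percentage for each cohort and time point, and then: "Antibody levels before the second vaccination and at 6, 11 and 18 months will be compared between each patient cohort and the non-cancer cohort". The tests are ANOVA or Kruskal-Wallis, followed by Welch t or Mann-Whitney U.

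Section 4.4 (Correction for drop-out) says that "we anticipate that there will be a drop-out of participants at later time points", and gives as possible reasons "death or poor performance status as a result of progressive malignancy and/or cancer treatment related AEs". Its response is a 20% increase in every cohort, which also has to cover participants seropositive at baseline.

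Section 10 removes baseline seropositives and unvaccinated participants from the immune analyses. It gives no method for missed visits or deaths. Section 8.6 continues sampling unless consent is withdrawn. Section 10.3 plans, as an example among other parameters, an analysis of "antibody decay after day 28", without saying how it is computed. Section 1.8 describes the 11- and 18-month visits as cross-sectional and notes that most participants will have had extra vaccinations by January 2022.

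**The concern.** All the named tests work at one time point and drop anyone without a sample there. The reasons for drop-out in section 4.4 are consequences of cancer or its treatment, so they concern B, C and D far more than the partners in A. A larger sample protects precision but does not change who is left. Continued sampling under section 8.6 cannot help when a participant has died or is too ill to attend.

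If leavers differ from stayers in antibody level, the 6-month contrast with cohort A mixes durability with selection. Each participant's day-28 value would show much of that selection and is collected before later losses, but the section 10.2 tests at 6 months do not use it. At stake is a secondary conclusion that will be used to counsel patients and to identify those who need other protection.

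**Working it through.** **1. The plan's own attrition figure.** Section 4.4 starts from 112 (B vs A) and 205 (C or D vs A) per group. 112 × 1.2 = 134.4, rounded up to 135; 205 × 1.2 = 246. Both match the plan. This is the only attrition allowance in the documents. It is not split by visit or cohort and applies to A as well. Section 1.6 adds an observed figure: 791 enrolled and 743 evaluable at day 28, so 48/791 = 6.1% not evaluable for all reasons. That is not a 6-month rate.

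**2. Assumed inputs (none is in the documents).** SD of log10 IgG 0.5. Correlation ρ between day 28 and the later visit 0.6 or 0.8. Patient drop-out 10%, 20% or 30%, and none in A. Odds ratio (OR) of drop-out per SD lower day-28 IgG 0.67, 1, 1.65 or 2.72.

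**3. Formulae.** With z the standardised day-28 log IgG, logit P(drop-out) = a − ln(OR) × z, where a is solved to give the stated drop-out. The stayers' mean is δ = E[z | stays]. The later-visit mean among stayers is shifted by ρδ SD, so observed GMC / full-cohort GMC = 10^(0.5 × ρ × δ).

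**4. Results.**

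| Drop-out | OR | δ (SD) | GMC ratio, ρ = 0.6 | GMC ratio, ρ = 0.8 |
|---|---|---|---|---|
| 10% | 0.67 | −0.039 | 0.973 | 0.964 |
| 10% | 1.65 | 0.049 | 1.034 | 1.046 |
| 10% | 2.72 | 0.091 | 1.065 | 1.087 |
| 20% | 0.67 | −0.078 | 0.947 | 0.931 |
| 20% | 1.65 | 0.096 | 1.069 | 1.093 |
| 20% | 2.72 | 0.173 | 1.127 | 1.173 |
| 30% | 0.67 | −0.116 | 0.923 | 0.898 |
| 30% | 1.65 | 0.143 | 1.104 | 1.141 |
| 30% | 2.72 | 0.253 | 1.191 | 1.262 |

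Example, last cell: 10^(0.5 × 0.8 × 0.253) = 10^0.101 = 1.26. At OR 1, δ = 0 and the ratio is 1.000 throughout.

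**5. Effect on the test.** In a simulation of 205 patients against 205 controls (ρ = 0.8, two-sided 5%, 2,000 runs), the true patient deficit was 0.30 SD. When drop-out was unrelated to level (OR 1), power was 0.81 at 20% drop-out and 0.79 at 30%. With 20% to 30% drop-out and OR 1.5 to 3, the attendee comparison showed a deficit of only 0.24 to 0.09 SD, and power fell to between 0.61 and 0.13. Regression on the day-28 values of all patients returned −0.30 SD in every case. It does so because drop-out in the simulation depends only on the observed day-28 level, which is the missing-at-random condition.

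**The case against.** The strongest reply has four parts.

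- **Direction.** A reader might infer that patients' persistence will look better than it is. That requires leavers to have lower antibody levels, and the documents do not link illness or drop-out to IgG. The range spans zero and changes sign at OR 0.67. This stands.
- **Day-28 value and decay.** A reader might infer that day-28 values go unused, or that decay will compare two different sets of people. Section 10.3 does plan decay after day 28, and section 10 promises all individual data points. What stands is narrower: the section 10.2 comparisons at later visits do not use day 28, and section 10.3 leaves the computation open. Plots of attendees do not correct for those absent.
- **Later visits.** Entry requires "Life expectancy > 12 months" while sampling runs to 18 months, and it is tempting to use this as evidence. It bears on the 18-month visit, not on month 6. Section 1.8 makes months 11 and 18 cross-sectional by design, so describing attendees fits that aim. Section 10.2 nevertheless lists those visits under longevity. The visit before the second vaccination is hardly affected.
- **Replacing the tests.** The level among living attendees is a legitimate target, and a mixed model gives a hypothetical value for those who died. Enrolment ended on 12 March 2021, and section 1.8 places month 11 in February 2022, so the 6-month samples were probably due in autumn 2021. Both facts favour adding a model over replacing the stated tests.

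**Conclusion.** The concern holds as a limitation of a secondary analysis. Section 10.2 assesses 6-month durability on attendees only, section 4.4 expects cancer-related losses, and the only provision is a larger sample. If drop-out is related to antibody level, the comparison with cohort A is biased. Under the assumed inputs the later patient GMC is off by about -10% to +26%. At 10% drop-out the range is about -4% to +9%, and there is no bias if drop-out is unrelated to level. These figures rest on the assumed SD, correlation, drop-out and odds ratios, and on no loss in A. The documents do not support a claim that patients' durability will in fact be overstated. The day-28 primary endpoint and its sample size are not touched.

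**What to change.** 1. For the two-dose question up to 6 months, add beside the tests in section 10.2 a likelihood-based mixed model on log IgG: visits before the second vaccination, day 28 and 6 months; cohort by visit; unstructured covariance; only values taken before any third vaccination.
2. State in section 10.3 that decay after day 28 is computed from within-person paired samples.
3. Report numbers and reasons missing by visit and cohort, with the day-28 IgG of leavers beside that of stayers. This shows from data in hand whether drop-out is related to day-28 level, and in which direction.
4. State that the model estimate is hypothetical for participants who died.
5. Describe the 11- and 18-month comparisons as cross-sectional immune status among attendees, not as durability of two doses.

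The cost is SAP wording and one standard model on samples already scheduled. The downsides are reliance on log-normality and missing at random, and the need to label the model as added after the 6-month samples were due.

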#### 1.4 COVID-19 vaccination in patients with cancer

Patients with cancer have an increased risk for an adverse outcome of COVID-19 [13-15]. As a consequence, many patients strictly adhere to self-isolation, resulting in loneliness and loss of quality of life. Therefore, vaccination needs to be prioritized for these vulnerable patients. In addition, effective COVID-19 vaccination is of extreme importance to protect patients with cancer to continue care and cure. An immune response to vaccination would not only protect them from life-threatening COVID-19 but also allow close contact with their loved ones. Therefore, patients and patient organizations have already claimed prioritization of vaccination against COVID-19 for patients with cancer.

For proper protection against COVID-19 by vaccination, specific immune responses need to be induced. SARS-CoV-2 specific immune cells are essential to combat the virus. B cells are important for antibody responses to neutralize the virus, while CD8 positive T cells can specifically recognize and eradicate virus-infected cells. In addition, CD4 positive T cells are required for providing necessary help to B cells and CD8 positive T cells. Cancer immunotherapy activates T cells against cancer cells by blocking the interaction between Programmed Death 1 (PD1) and its ligand (PD-L1) [33]. How this treatment impacts immune responses to vaccination is unknown. Chemotherapy causes bone marrow suppression and reduces the number of immune cells in the blood circulation, which may hamper the induction of protective immune responses after vaccination as suggested in studies on

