#### 8.1.2 Secondary study parameters/endpoints

- Safety assessment through:
  - Incidence and severity of solicited AEs during 7 days after each vaccination (see Appendix 1)
  - o Incidence and nature of SAEs during 7 days after each vaccination
  - Incidence and nature of newly occurring irAEs [38] grade ≥ 3 in cohort B and D up to 28 days after the last vaccination graded according to the Common Terminology Criteria for Adverse Events version 5.0 (CTCAEv5.0)
  - Incidence, nature and severity of AESIs (see Appendix 2) graded according to CTCAEv5.0
- In depth assessment of immune response through:

- Measurement of SARS-CoV2 specific antibodies before the second vaccination to analyze initial response, and at 6 and 11 and 18 months after the second vaccination to measure longevity
- Measurement of SARS-CoV2 specific antibodies at day 28 after the third vaccination if applicable
- Assessment of SARS-CoV2 specific T cells response at 28 days after the second and third vaccination and at 6, 11 and 18 months after the second vaccination using a high throughput Interferon y ELIspot

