			28	180	Vacc3 ad	28	Day	540
			Vacc2			vacc3	330	
SARS-Cov-2	х	х	х	х	х	х	х	х
antibodies								
PBMC isolation	х		х	х	х	х	х	х
for in depth								
cellular								
immune								
response								
Routine	х	х	х	х	х	х	х	х
hematology b								
Routine	х	х	х		х	х		
chemistry c								

Table 2: Blood tests

PBMC = peripheral blood mononuclear cells

a Blood has to be drawn before vaccination

b Hemoglobin, red blood cell count, platelet count, white blood cell count, white blood cell differential

c glucose, creatinine, aspartate aminotransferase (ASAT), alanine aminotransferase (ALAT), albumin, lactate dehydrogenase (LDH), C-reactive protein (CRP).

d Only participants with an inadequate antibody response (≤300BAU/mL) on day 28 after the second vaccination.

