SARS-CoV-2 specific T cell response will be measured at baseline, and at 28 days after the second and third vaccination, and 6, 11 and 18 months after the second vaccination and expressed as the number of IFN-γ producing SARS-CoV2 specific T cells/million PBMC. To assess the contribution of CD8+ T cells in this response, we will assess the number of IFN-γ producing T cells after blocking with an MHC class I antibody. This will be expressed as the number of IFN-γ producing CD4+ T cells/ million PBMCs. Subtraction of the number of responding CD4+ T cells from the total number of responding T cells will lead to the number of IFN-γ producing CD8+ T cells/ million PBMCs. Results will be compared between each patient cohort and the cohort of individuals without cancer using ANOVA or Kruskal–Wallis one-way analysis of variance, and Welch t-tests or Mann-Whitney U tests, depending on the distribution of the data.

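### The between-cohort T cell comparison makes no stated use of the baseline ELISpot, and the per-million-PBMC scale alone cannot exclude a fall in circulating specific T cells

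*Combined protocol and SAP*

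**What the plan says.** Section 10.2 gives one unit for the ELISpot endpoint: it is "expressed as the number of IFN-γ producing SARS-CoV2 specific T cells/million PBMC". The CD4+ and CD8+ parts use the same denominator, and no per-volume unit appears.

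The same section plans a baseline sample: "SARS-CoV-2 specific T cell response will be measured at baseline, and at 28 days after the second and third vaccination". The analysis it then states is a comparison between cohorts: "Results will be compared between each patient cohort and the cohort of individuals without cancer using ANOVA or Kruskal–Wallis one-way analysis of variance", with Welch or Mann-Whitney tests. It states no change from baseline, fold-rise, baseline covariate or threshold for a T cell response. The endpoint list in section 8.1.2 gives only post-vaccination times: "Assessment of SARS-CoV2 specific T cells response at 28 days after the second and third vaccination and at 6, 11 and 18 months".

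Other parts of the plan bear on this:

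- Section 10.3 uses baseline for the antibody data, by "calculating geometric mean fold-rise between baseline and post-baseline time points and antibody decay after day 28". It has no counterpart for T cells.
- Section 1.4 says "Chemotherapy causes bone marrow suppression and reduces the number of immune cells in the blood circulation" and names this as a possible reason for a weaker response to vaccination.
- Table 2 in section 8.3 marks routine hematology, which includes "white blood cell count, white blood cell differential", at every visit where PBMC are isolated.
- Section 10 leaves baseline-seropositive participants out of all immune response analyses, and section 4.3 excludes confirmed infection.
- Section 1.8 describes the 11- and 18-month measurements as cross-sectional, to show immune status after extra vaccinations.

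**The concern.** Two features limit what the comparison of cohorts B, C and D with cohort A can show.

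The first is baseline. The cohorts are defined by treatment, not randomised (sections 3 and 8.2), and patients may already be on that treatment when the baseline sample is drawn. If T cell reactivity before vaccination differs between cohorts, a comparison of day-28 levels mixes that difference with the effect of vaccination. The secondary objective is the response after vaccination.

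The second is the denominator. Spots per million PBMC measure how frequent specific cells are among the mononuclear cells tested. They do not measure how many such cells circulate. Similar per-million results in cohorts C, D and A would therefore not by themselves answer the question that section 1.4 raises about fewer cells in the blood.

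**Working it through.** The plan states no sample size, effect size or SD for the T cell endpoint, so there is no figure of its own to reproduce. The numbers below are illustrations on assumed values; none come from the documents.

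**1. Denominator, all PBMC types falling in proportion.** Specific T cells per mL = (spots per million PBMC) × (PBMC in 10^6/mL). Let the per-million score be equal in patient and control.

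| PBMC retained | Per-million ratio, patient/control | Per-mL ratio |
|---|---|---|
| 75% | 1.00 | 0.75 |
| 50% | 1.00 | 0.50 |
| 25% | 1.00 | 0.25 |

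With assumed counts of lymphocytes plus monocytes of 2.3 × 10^6/mL (control) and 1.3 × 10^6/mL (patient), and 100 spots per million in both:

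- Control: 100 × 2.3 = 230 per mL.
- Patient: 100 × 1.3 = 130 per mL.
- Deficit: 1 − 130/230 = 43%.
- For patient counts of 1.8 to 1.0 × 10^6/mL: 1 − 1.8/2.3 = 22% to 1 − 1.0/2.3 = 57%.

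**2. Denominator, T cells falling more than the rest.** Let T cells be 60% of PBMC and fall to half, with the specific share among T cells unchanged. The per-mL ratio is 0.50.

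- Other PBMC at 75%: T cell share = 0.30/(0.30 + 0.30) = 0.50; per-million ratio = 0.50/0.60 = 0.83.
- Other PBMC at 100%: T cell share = 0.30/(0.30 + 0.40) = 0.43; per-million ratio = 0.43/0.60 = 0.71.

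The loss then shows, but only in part.

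**3. Baseline.** Let day-28 level = baseline + vaccine-induced part, with induced parts of 100 (control) and 50 (patient) per million, a true difference of 50.

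| Baseline, control | Baseline, patient | Raw day-28 difference | Raw ratio |
|---|---|---|---|
| 0 | 0 | 50 | 0.50 |
| 20 | 20 | 50 | 0.58 |
| 50 | 50 | 50 | 0.67 |
| 20 | 0 | 70 | 0.42 |
| 0 | 20 | 30 | 0.70 |

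An equal baseline leaves the mean difference intact, although it moves the ratio. Unequal baselines bias the difference in either direction.

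**4. Which use of baseline.** With equal SDs and pre/post correlation r, the variance relative to the raw level is 1 − r² for the baseline-adjusted level and 2(1 − r) for the change score.

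| r (assumed) | Adjusted level | Change score |
|---|---|---|
| 0.2 | 0.96 | 1.60 |
| 0.5 | 0.75 | 1.00 |
| 0.7 | 0.51 | 0.60 |

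For r of 0.2 to 0.5, adjustment saves 4–25% of the variance, while the change score gains nothing and can be 60% worse. Adjustment has a limit: it removes the slope times the baseline gap, and with equal SDs the slope is r. If a gap of 20 carried through in full to day 28, adjustment at r = 0.5 would remove 0.5 × 20 = 10 of it. Baseline levels by cohort should therefore be shown beside the adjusted result.

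**The case against.** The plan has real safeguards. Baseline T cells are measured, and section 10 promises all individual data points for secondary parameters, so an imbalance could be seen. Section 10.3 relates baseline immune parameters to response. Excluding baseline-seropositive participants and confirmed infections removes much of the obvious pre-existing reactivity, and a baseline common to the cohorts cancels in a mean difference.

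A reader might infer that the plan ignores the baseline sample and counts pre-existing reactivity as vaccine response. The documents do not support that. The sample is collected, no T cell responder rule is defined under which anyone would be counted, and bias in the mean difference needs unequal baselines. What stands is narrower. The exclusions screen antibody status and infection history, not T cell reactivity in seronegative participants, and nothing makes that reactivity equal across non-randomised cohorts.

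A reader might also infer that the unit divides out the very cell loss the trial sets out to study. Section 2 does not list cell loss as an objective; it is a mechanism in the rationale, and impaired induction could still show as a lower frequency. Full concealment needs all PBMC types to fall in proportion.

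The per-mL scale is also a different quantity, not a correction. Section 4.2 allows the last chemotherapy at any time within 4 weeks of vaccination, and Table 1 times visits from vaccination. Per-mL values would therefore vary with the point in the treatment cycle. That objection stands, and it limits the per-mL analysis to a supportive role.

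**Conclusion.** The point holds as a modest gap in a secondary analysis. Per million PBMC is the only unit, and the baseline ELISpot has no stated role in the cohort comparison, although the data for a better analysis are already scheduled. The day-28 contrast is biased to the extent that baseline reactivity differs between cohorts among seronegative participants. A per-million result alone cannot exclude a fall in circulating specific cells.

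The size cannot be derived from the documents. The 22–57% deficits restate assumed PBMC counts under an assumed equal score, and the baseline examples are likewise assumed.

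Section 1.6 should not be read as using T cells to judge protection. It reports only that responses were detected in almost half of the suboptimal and non-responders, and eligibility for the third vaccination rests on antibody level. The primary endpoint and the sample size are unaffected.

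**What to change.** In section 10.2:

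- Keep spots per million PBMC as the main scale for total, CD4+ and CD8+ responses.
- For day 28 after the second vaccination, specify the between-cohort comparison as the log level adjusted for the baseline value, not the raw change score. State how zero counts are handled on the log scale, and tabulate baseline levels by cohort. Label this post hoc where day-28 results are already reported (section 1.6).
- Keep raw levels at months 11 and 18, where current immune status is the aim (section 1.8). Say which approach applies at month 6.
- Add a supportive analysis of specific T cells per mL: spots per million PBMC × same-visit lymphocytes plus monocytes in 10^6/mL. State that it measures circulating number rather than frequency, and that it varies with time since the last chemotherapy cycle.

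Reconcile section 8.1.2, which omits baseline for this endpoint, with section 10.2.

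The cost is plan wording and one derived variable; no new visits or samples are needed. The downside is a second scale to report. Participants without a baseline PBMC sample drop out of the adjusted comparison, and those without a same-visit differential drop out of the per-mL analysis.
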